9.4.3 ANALYSIS OF THE SECONDARY ENDPOINT(S)

Secondary endpoints:

Effectiveness of the radon app vs. brochure at 3 months re: changes in radon knowledge, as measured by the number of correct responses to a series of 20 true/false questions (e.g., "The EPA recommends that homes with 4 picocuries per liter (pCi/L) or more of radon should be fixed.").

Radon knowledge will be measured by the number of accurate responses to 20 True-False statements in T1 (baseline) and T2 (at 3 months).¹¹ The response options will be: "true," "false," and "I don't know." Participants' responses to each statement will then be re-coded to 1 ("correct") or 0 ("incorrect" or "I don't know"). After that, two radon knowledge index variables (continuous) will be created by summing participants' responses to each statement in T1 (baseline) and T2 (at 3 months). Lower numbers on index variables indicate a low level of knowledge, whereas higher numbers indicate greater knowledge.

H₀: There will be no changes in radon knowledge among those assigned to the radon app condition and those assigned to the brochure condition. **H₁**: There will be more positive changes in radon knowledge among participants assigned to the radon app condition. **Statistical test**: Differences in radon knowledge between the two groups will be tested with directional, independent t-tests, with SAS.

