Description of Study Intervention/Experimental Manipulation:	
An online experiment with two experimental conditions using a pretest-posttest design: the radon app condition vs. brochure condition. Participants in both experimental conditions will complete an online pre-exposure survey during the baseline phase of the study. Upon completion of the pre-exposure survey, participants assigned to the radon app condition will be asked to install the radon app on their smartphones and use the app for three months. App installation will be verified electronically via text message sent to the investigators. To make the informational content of the radon app and EPA brochures equivalent, the informational content in the app condition will be repurposed from EPA brochures used in the brochure condition. Participants in the radon app condition will have the opportunity to order a free radon test kit through the app at any time during the three-month period.
 
In contrast, individuals assigned to the brochure condition will receive three EPA brochures for the three-month period via postal mails. These brochures are (1) Basic radon facts (https://bit.ly/2S6ryFw); (2) A citizen's guide to radon (https://bit.ly/3l3FhcJ); and (3) Consumer's guide to radon reduction (https://bit.ly/3ibt83n). In each mailing, participants will receive a pre-addressed, pre-paid postcard to request a free radon test kit. The postcard will be addressed to a UND address so that we can track the number requested by participants in the brochure condition.

Study Duration* :	6 months.
Participant Duration:	3 months.

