completing the pre-exposure survey. Once the app is installed in participants' own phones and they successfully log in through their Twitter credentials, they will be asked to keep the app on their phone for three months with the notification setting "on". After all these steps are completed, they will be asked to complete the pre-exposure survey. The radon app can be accessed via computer or smartphone: <https://radon-production.herokuapp.com/>

The other half of the participants assigned to the brochure condition will be asked to provide the mailing address prior to completing the pre-exposure survey so that they can receive EPA brochures in the next 3 months via postal mail. Once this step is completed, they will be asked to complete the pre-exposure survey. During the 3-month period, participants assigned to the radon app condition will receive the radon educational materials via the app. Materials include the informational content repurposed from EPA brochures and radon-education Tweets using hashtags, such as #radon, #lungcancer, #healthylungs, and #radonawareness. The app uses the Twitter's mechanism so that's why participants need to use their Twitter credentials to login, and those hashtags used in Tweets are automatically detected by the app, and will be populated in the app. While keeping the app for three months, if participants would like to test their homes for radon levels, as education materials they will be exposed to encourage to do so, they can request a free radon kit through the app. They will be asked to enter their mailing address, email, and phone number so that the kit will be delivered to their home address. Although the app would collect such personal information, this is only to provide them with the free radon kit, and such information won't be attached to their any survey responses. On the other hand, participants assigned to the brochure condition will receive a total of three EPA brochures, with each one being delivered once a month. In each mailing, participants will receive a pre-addressed, pre-paid postcard to request a free radon test kit. The postcard will be addressed to a UND address so that we can track the number requested by participants in the brochure condition.

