9 STATISTICAL CONSIDERATIONS

9.1 STATISTICAL HYPOTHESES

- Primary Endpoint(s): **H₀**: The incidence of: (a) participants' requests for free radon kits and (b) participants utilizing the test kits and returned to Alpha Energy Labs among those assigned to the radon app condition and those assigned to the brochure condition will not differ. **H₁**: The incidence of: (a) participants' requests for free radon kits and (b) participants utilizing the test kits and returned to Alpha Energy Labs will be higher among those assigned to the radon app than the brochure condition.

H₀: The difference in the incidence of request for and utilization of radon test kits between the radon app and brochure conditions will not be affected by participants' gender, age, race, smoking status, or geographic location (state/county of birth). **H₁**: There is significant interaction between the radon app and brochure conditions and the variables above in terms of the proportion requesting and utilization of test kits.

- Secondary Endpoint(s): **H₀**: There will be no changes in radon knowledge among those assigned to the radon app condition and those assigned to the brochure condition. **H₁**: There will be more positive changes in radon knowledge among participants assigned to the radon app condition.

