9.2 SAMPLE SIZE DETERMINATION

Primary endpoints:

1. Number of radon test kits requested by participants in the radon app and brochure conditions; and
2. Number of radon test kits used and returned to the laboratory by participants in the two conditions.

Secondary endpoints:

Effectiveness of the radon app vs. brochure at 3 months re: changes in radon knowledge, as measured by the number of correct responses to a series of 20 true/false questions (e.g., “The EPA recommends that homes with 4 picocuries per liter (pCi/L) or more of radon should be fixed.”).

Sample size determination:

A sample size of at least 100 people in each group will have a power of .8 to .9 to detect differences in proportions of at least 20%, Chi-square values of five or more with one or two degrees of freedom, mean differences of at least 0.3, and odds ratios greater than three in logistic regression.

Statistical analyses:

H₀: The incidence of: (a) participants’ requests for free radon kits and (b) participants utilizing the test kits and returned to Alpha Energy Labs among those assigned to the radon app condition and those assigned to the brochure condition will not differ. **H₁**: The incidence of: (a) participants’ requests for free radon kits and (b) participants utilizing the test kits and returned to Alpha Energy Labs will be higher among those assigned to the radon app than the brochure condition. **Statistical test**: We will use a directional Z test for difference in proportions to determine whether the incidence of requested and returned kits is higher for those assigned to the radon app condition with SAS. Differences will be described using absolute and relative differences in proportions.

H₀: There will be no changes in radon knowledge among those assigned to the radon app condition and those assigned to the brochure condition. **H₁**: There will be more positive changes in radon knowledge among participants assigned to the radon app condition. **Statistical test**: Differences in radon knowledge between the two groups will be tested with directional, independent t-tests, with SAS.

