9.4.7 SUB-GROUP ANALYSES

Primary endpoints will be analyzed based on gender, age, race, smoking status, or geographic location (state/county of birth):

H₀: The difference in the incidence of request for and utilization of radon test kits between the radon app and brochure conditions will not be affected by participants' gender, age, race, smoking status, or geographic location (state/county of birth). **H₁**: There is significant interaction between the radon app and brochure conditions and the variables above in terms of the proportion requesting and utilization of test kits. **Statistical test**: We will use multivariate regression analyses predicting incidence of requesting and utilization of test, while controlling for gender, age, race, smoking status, location, and time spent using the app with SAS. Interactions will be tested in multivariate models and significant interactions will be described by levels of univariate Z or chi-square tests.

Secondary endpoints will not be analyzed based on gender, age, race, smoking status, or geographic location (state/county of birth).

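### The radon knowledge test leaves the collected baseline score out as a covariate, does not name the variable it compares, and is paired with a null hypothesis it does not test

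*Combined protocol and SAP*

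**What the plan says.** Section 9.4.3 scores 20 true/false items at baseline (T1) and at three months (T2), and "two radon knowledge index variables (continuous) will be created by summing" the item scores at each time. No change score is derived. The test is then given in one sentence, which section 9.2 repeats: "Differences in radon knowledge between the two groups will be tested with directional, independent t-tests, with SAS".

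The endpoint is worded as changes in knowledge, and the alternative hypothesis reads "There will be more positive changes in radon knowledge among participants assigned to the radon app condition". The null hypothesis, in sections 9.1, 9.2 and 9.4.3, reads "There will be no changes in radon knowledge among those assigned to the radon app condition and those assigned to the brochure condition".

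Section 9.4.1 defers covariates to later sections, but 9.4.3 names none. The only covariate list is in 9.4.7. It serves the two kit endpoints and does not include T1 knowledge.

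Section 9.2 claims power of .8 to .9 with at least 100 per group for, among other effects, "mean differences of at least 0.3". It gives no unit, SD or alpha.

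**The concern.** There are three linked defects.

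- **Unused covariate.** T1 is the same 20-item scale as the outcome, measured on the same people. Leaving it out as a covariate gives up precision that costs nothing to recover.
- **Undefined variable.** The endpoint and the alternative point to T2 − T1, but the test sentence names neither that nor T2. The two t-tests can give different p-values from the same data, so the analyst has a choice on the only secondary endpoint.
- **Mismatched null.** The written null says nothing changes in either arm. If both arms learned equally, it would be false although the app had no advantage.

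At stake are the precision of the knowledge comparison and a clear statement of what it tests. The validity of the test is not at stake, provided T1 was measured before exposure.

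**Working it through.** **Inputs from the documents:** two arms with at least 100 each (9.2), taken as equal allocation; a directional test (9.2, 9.4.3); a mean difference of 0.3 (9.2).

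**Assumptions, because the documents are silent:** 0.3 is in SD units of T2; one-sided alpha is 0.05; the T1–T2 correlation r is 0.3, 0.5 or 0.7; the SDs are equal unless stated otherwise.

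**The plan's own figure.** For a T2-only t-test the noncentrality is 0.3 × √(100/2) = 2.12, which gives power of 68% (56% two-sided). The stated .8 to .9 is not reproduced on these assumptions; one-sided alpha of 0.10 gives 80%. That is a separate matter, but it shows there is no power to spare.

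**Variance factors.** Let k = SD(T1)/SD(T2). In units of the T2 variance:

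- T2-only t-test: 1
- change-score t-test: 1 + k² − 2rk
- ANCOVA: 1 − r²

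Change score minus ANCOVA is (k − r)², and T2-only minus ANCOVA is r². Neither can be negative, so apart from one degree of freedom ANCOVA never does worse, whatever r and k are.

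**Equal SDs (k = 1), 100 per arm, difference 0.3 SD, one-sided 5%, noncentral t:**

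| | r = 0.3 | r = 0.5 | r = 0.7 |
|---|---|---|---|
| Change-score factor | 1.40 | 1.00 | 0.60 |
| ANCOVA factor | 0.91 | 0.75 | 0.51 |
| Reduction versus change score | 35% | 25% | 15% |
| Reduction versus T2-only | 9% | 25% | 49% |
| Change-score n per arm matching ANCOVA with 100 | 154 | 133 | 118 |
| Power, T2-only | 68% | 68% | 68% |
| Power, change score | 56% | 68% | 86% |
| Power, ANCOVA | 72% | 79% | 91% |

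The matching n is 100 × change-score factor / ANCOVA factor; for example 100 × 1.40/0.91 = 154.

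**Unequal SDs.** For the same three values of r, the reduction versus the change score is 58.3/53.5/51.0% if SD(T2)/SD(T1) = 0.7, and 19.5/8.8/0.9% if it is 1.3. The matching n then runs from 100/(1 − 0.009) ≈ 101 to 100/(1 − 0.583) ≈ 240.

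**Validity.** In 20,000 simulated trials with r = 0.5, k = 1 and no arm difference, rejection rates were 4.9% (T2-only), 5.2% (change score) and 5.0% (ANCOVA). With a 0.3 SD difference they were 67.7%, 68.0% and 78.4%.

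**The null.** With both arms improving equally by 1 SD (r = 0.5, 20,000 trials), the written null is false, yet the change-score t-test rejects in 5.1% of trials, its nominal rate. What it tests is equal change between arms.

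**Timing of T1.** Section 5.5 has app participants install the app and log in first: "After all these steps are completed, they will be asked to complete the pre-exposure survey". Section 1.1 has the opposite order: "Upon completion of the pre-exposure survey, participants assigned to the radon app condition will be asked to install the radon app on their smartphones". Sections 4.1, 6.1.1 and 8.1 agree with 1.1. Suppose exposure had raised T1 by 0.3 SD in the app arm only, with k = 1 and T2 otherwise unaffected. The estimated app effect would be biased by −0.30 SD with the change score, by −r × 0.3 = −0.09/−0.15/−0.21 SD with ANCOVA, and by 0 with T2 alone.

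**The case against.** The strongest reply is that this is a preference for efficiency on a secondary endpoint. An unadjusted t-test is simple and valid under randomization. The endpoint and the alternative both speak of changes, so the natural reading is T2 − T1, which already uses T1 by subtraction. The null is loosely worded, but the test sentence and the alternative are plainly between-arm, so no result need be misread. The size of the gain rests on assumed values and is practically nil in one corner (0.9% at r = 0.7 with an SD ratio of 1.3).

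Much of this stands. The t-test is valid, the null is a matter of wording, and the gain is uncertain in size; the 118–154 per arm applies to equal SDs only. It does not remove the point. A change score fixes the T1 slope at 1 and is never more precise than ANCOVA apart from one degree of freedom. The variable is still not named where the test is specified. The covariate is already collected.

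It is also fair to say that parts of the protocol are in the past tense, so data may already exist, and a change of test made after outcomes by arm are seen would be post hoc. That bears on when the change is made, not on whether it is right. The contradiction over installation order is a separate matter and enters here only as a condition on using T1.

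**Conclusion.** The concern holds. The planned knowledge analysis is an unadjusted directional t-test on an unnamed variable, with a null hypothesis that does not match it. Provided T1 preceded exposure, the cost is precision, not bias. With equal SDs and r of 0.3 to 0.7, ANCOVA variance is 15–35% below the change-score t-test and 9–49% below the T2-only t-test; across SD ratios of 0.7 to 1.3 the saving over the change score is 1–58%. The direction follows from the algebra; the size depends on r, the SD ratio, the alpha and the reading of 0.3 as SD units, none of which the documents give. The change should be made, but the planned test would not be invalid without it.

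**What to change.** In 9.4.3 and 9.2, replace the t-test sentence with: *The T2 index will be analysed in a linear model with arm and T1 index (ANCOVA); the app-minus-brochure adjusted mean difference will be tested with the planned directional test and reported with its confidence interval.*

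In 9.1, 9.2 and 9.4.3, reword the null as *mean T2 knowledge, adjusted for T1, does not differ between arms* and the alternative as *is higher in the app arm*.

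Two conditions come first:

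- Confirm that T1 was completed before app exposure, and reconcile 5.5 with 1.1, 4.1, 6.1.1 and 8.1.
- Confirm that T1 and T2 can be linked per participant. Section 8.1 keeps addresses apart from the survey responses; 10.1.3 provides a study identification number.

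If T1 followed exposure, use it neither as a covariate nor in a change score. If either condition fails, name the directional t-test on T2 alone, which needs neither, and drop the words on adjustment from both hypotheses.

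Make the change as a dated amendment before outcomes by arm are seen; otherwise label the analysis post hoc.

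The cost is text edits in three sections and one model term in SAS. If T1 has already been collected after exposure or without a link, no edit can restore it and the T2-only fallback applies. This fix does not deal with missing T2 scores, the unstated alpha or the stated power.

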9.4.4 SAFETY ANALYSES

N/A

9.4.5 BASELINE DESCRIPTIVE STATISTICS

N/A

9.4.6 PLANNED INTERIM ANALYSES

N/A

9.4.7 SUB-GROUP ANALYSES

Primary endpoints will be analyzed based on gender, age, race, smoking status, or geographic location (state/county of birth):

H₀: The difference in the incidence of request for and utilization of radon test kits between the radon app and brochure conditions will not be affected by participants' gender, age, race, smoking status, or geographic location (state/county of birth). **H₁**: There is significant interaction between the radon app and brochure conditions and the variables above in terms of the proportion requesting and utilization of test kits. **Statistical test**: We will use multivariate regression analyses predicting incidence of requesting and utilization of test, while controlling for gender, age, race, smoking status, location, and time spent using the app with SAS. Interactions will be tested in multivariate models and significant interactions will be described by levels of univariate Z or chi-square tests.

Secondary endpoints will not be analyzed based on gender, age, race, smoking status, or geographic location (state/county of birth).

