2.2 BACKGROUND

In collaboration with a media services company (Triad Interactive Media, Greensboro, NC), we developed a radon app for smartphones.¹¹ Briefly, the app uses a framework in HTML5 and the open source Twitter API. Posts created by the app are cross-listed on Twitter. Once users log in via Twitter, they can view radon news and mobile-friendly informative content on radon repurposed from EPA brochures. Users also can access existing Tweets containing hashtags, e.g., #radon, #radonawareness, #radonmitigation, and #lungcancer. Individual users' activities on the radon app, along with their Twitter handle, are saved on Triad Interactive Media's server. Through the app, users could order a free radon test kit at any time.

We conducted a pilot clinical trial using this app. Ninety six (96) undergraduates at the University of North Dakota in Grand Forks, ND (UND) were assigned to use the radon app for one month and were tested on several aspects of radon knowledge and testing using a pretest-posttest design.¹¹ We have recently published our findings.¹¹ We found that the use of the radon app: (1) significantly improved individuals' radon knowledge and generated positive attitudes toward radon testing; (2) significantly increased self-efficacy (i.e., an individual's perceived capability to order a radon test kit and use it); (3) significantly increased response efficacy (i.e., an individual's evaluation of the effectiveness of radon testing in preventing radon exposure); and (4) resulted in 24% of study participants ordering a free radon test kit. However, only a small percentage of participants actually used the test kit they obtained (i.e., employed the test in their home and returned it to the lab; a total test completion rate of 9%).

In summary, our pilot trial demonstrated that the radon app improved radon knowledge, motivation to test, and stimulated requests for free test kits. However, our pilot trial had a key limitation: there was no control group (i.e., a group not exposed to the app). Our present research builds and improves upon these preliminary findings. To do so, we will include a control group that receives usual care (radon information communicated via EPA brochures).

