6.2 FIDELITY

6.2.1 INTERVENTIONIST TRAINING AND TRACKING

Ideally, the fidelity of delivery would be monitored by measuring the amount of time persons in the experimental group spent time on the smartphone app. However, this functionality was not developed for financial reasons (the app developer required more money that we had to spend), nor was there any parallel for the comparison group, since there was no way to guarantee that they had indeed read the brochures we sent. However, we did verify the downloading of the app to the experimental group.

With regard to adherence, this was measured indirectly, via the percentage correct of tests of radon knowledge.

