6.4 STUDY INTERVENTION/EXPERIMENTAL MANIPULATION ADHERENCE

Participants' adherence with study procedures for the radon app condition will be tracked based on the back-end data provided by the app development company, Triad Interactive Media. A complete adherence is not expected, however, because participants were asked to use the app occasionally as they would do for other apps. Participants' adherence with study procedures for the brochure condition will be tracked based on the number of returned postal mails. A 100%

delivery of postal mails is not expected, however, because delivery failure reflects the real-life situations participants would face in other situations.

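### The subgroup interaction models in section 9.4.7 adjust for time on the app, a post-randomisation variable that exists by design only in the app arm and that section 6.2.1 says could not be measured

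*Combined protocol and SAP*

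**What the plan says.** Section 9.1 places an interaction hypothesis under the primary endpoints: the app-versus-brochure difference in kit requests and kit use may vary with gender, age, race, smoking status or geographic location. Section 9.4.7 is its only test. It fits regressions for both outcomes "while controlling for gender, age, race, smoking status, location, and time spent using the app with SAS" and says interactions are tested in multivariate models. No other model is described. Section 9.4.1 promises that covariates will be pre-specified in later sections, and 9.4.7 is the only one that lists any.

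On whether app time is available:

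- Section 6.2.1 calls "measuring the amount of time persons in the experimental group spent time on the smartphone app" the ideal way to monitor fidelity, then says "this functionality was not developed for financial reasons", "nor was there any parallel for the comparison group". What was verified is that the app was downloaded.
- Section 6.4 says app-arm adherence "will be tracked based on the back-end data provided by the app development company".
- Section 2.2 says users' "activities on the radon app, along with their Twitter handle, are saved on" the developer's server. Neither 2.2 nor 6.4 says that time is recorded.
- Section 6.3 restricts download to the app arm, although section 5.5 also gives a web address for the app. Under section 4.1, app participants order kits through the app.
- Section 9.3 requires all randomised participants in the analyses.

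No section gives an app-time value for brochure participants.

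**The concern.** A covariate in a between-arm model should be fixed before randomisation. App time is a consequence of assignment and a likely route to the outcome, so adjusting for it removes part of the effect being studied. In an interaction model the damage takes a particular form. If one subgroup uses the app more, adjustment can hide a real difference between subgroups or create one where the randomised effects are equal.

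The plan also relies on a variable that another section says was not captured, and it leaves the brochure-arm value open. An analyst would have to choose the coding after the data are in, for the only test of a hypothesis listed with the primary endpoints.

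**Working it through.** **The plan's own figure.** Section 9.2 claims power of 0.8 to 0.9 for a 20-point difference with 100 per arm. No alpha is stated. At an assumed two-sided 0.05 this gives 0.812 for 40% vs 60% and 0.910 for 15% vs 35%, so the range reproduces for mid-range rates. It concerns the main comparison and does not bear on this point.

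**The model.** Let A be arm (1 = app), G a binary subgroup factor and T app time:

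logit P(Y = 1) = b0 + b1·A + b2·G + b3·A·G + b4·T

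**Reading 1: T unrecorded, or missing in the brochure arm.** If T is unrecorded, no row is complete. If it is missing only for brochure participants, complete-case fitting keeps 100 of 200 rows, all with A = 1. The A column then equals the intercept and A·G equals G. The five columns have rank 3, so b1 and b3 are not estimable. No control is kept, contrary to section 9.3. Substituting the verified download does not help: if every app participant installs, it is identical to A (rank 4 of 5).

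**Reading 2: T = 0 in the brochure arm.** The rank is 5 of 5 and the model fits. But b1 is now the arm contrast at zero use, and b3 compares the levels of G at equal use. With mean app use μ1 and μ0 in the two levels, to first order:

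randomised interaction ≈ b3 + b4·(μ1 − μ0)

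The two agree only if b4 = 0 or μ1 = μ0.

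**Inputs for a size.** From section 2.2, the app request rate is 24% ("resulted in 24% of study participants ordering a free radon test kit") and the rate of tests used and returned is 9% ("a total test completion rate of 9%"). Everything else is assumed: brochure request rate 5, 10 or 15%; G split 50/50; app time Gamma(2,1), mean 2, rescaled so that one level has twice the use of the other with overall mean use fixed (means 4/3 and 8/3); 100 per arm; two-sided 5% test; 3,000 simulated trials per scenario; medians over converged fits.

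**(a) Real interaction, effect wholly through use.** The slope on T is solved so that the app arm's overall request rate is 24%.

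| Brochure rate | Slope | Interaction OR without T | with T | Rejection without T | with T |
|---|---|---|---|---|---|
| 5% | 0.78 | 2.95 | 1.04 | 12.3% | 2.1% |
| 10% | 0.47 | 2.00 | 0.99 | 11.4% | 3.3% |
| 15% | 0.27 | 1.54 | 1.03 | 8.8% | 5.2% |

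Hand check at 10%: exp(0.47 × 4/3) = exp(0.63) = 1.87, near the population value of 1.93. With half the effect through use, ORs of 1.83/1.38/1.20 become 0.98/0.96/1.01. With full mediation the arm OR of 6.3/2.9/1.8 becomes about 1.0, though 9.4.7 does not formally test the arm term.

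**(b) No true interaction.** Both app levels request at 24%, the brochure rate is 10%, use differs two-fold, and use has log-OR 0.3 or 0.6 per unit.

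| Log-OR of use | Interaction OR without T | with T | False rejection without T | with T |
|---|---|---|---|---|
| 0.3 | 1.0 | 0.62 | 3.8% | 7.4% |
| 0.6 | 1.0 | 0.37 | 4.0% | 17.8% |

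Hand check at 0.6: holding both levels at 24% implies zero-use request rates of about 12% and 5%, so the OR at equal use is (0.05/0.95)/(0.12/0.88) = 0.39. With 1.5-fold use, false rejection is 5% or 9%.

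**(c) Equal use in both levels.** Rejection barely changes (3.5% vs 3.8%, and 3.9% vs 4.1% at log-OR 0.6).

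**(d) Use unrelated to outcome.** The standard error of the interaction rises by at most 4%, and that of the arm term 1.2 to 1.4-fold.

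**A different mechanism.** If app time has no effect but marks motivation, and one level uses the app twice as long, the large-sample interaction OR moves from 1.00 to 0.48. At 100 per arm, false rejection goes from 4.1% to 12.9%.

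**Kit use, 9% vs an assumed 3% or 5%.** About 40–43% or 16–19% of interaction fits do not converge, with or without T. In cases (a) and (d) rejection is about 1–3% either way. With no true interaction and log-OR 0.6, rejection goes from 0.6% or 1.6% to 6.5% or 11.2% of converged fits.

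**The case against.** The best case against rests on four points.

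1. Section 9.4.7 goes on to describe significant interactions level by level with univariate tests. These carry no app time and keep the randomised comparison within each level. This limits the harm in what is finally described. It does not protect the test that decides which interactions count as significant.
2. The documents make the unmeasured reading at least as likely as zero coding. A model that fails is visible, unlike a biased one, and every odds ratio above assumes that time exists and is coded 0. This is fair: the contradiction between 6.2.1 and 9.4.7 is certain, and the sizes are conditional. But the failed model is still the only pre-specified test, and a back-end activity proxy would still be post-randomisation and confined to the app arm.
3. The false-positive case depends on chosen inputs. No document supports a two-fold difference in use. At 1.25-fold use, false rejection is 5.0% or 5.8%. Scaling matters too: if one level's use is doubled without holding mean use fixed, the two-fold figures are about 11–12% and 31–32%. The figures show direction and a plausible range, not a forecast.
4. The analysis is of limited weight. It is absent from the objectives, interaction power for kit requests is only about 9–12% without app time, and sparse data dominate for kit use. All of this stands and keeps the point well short of threatening the trial.

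Section 9.4.7 also does not say outright that the interaction models use the same covariate list. That is the natural reading, and no other list is given.

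**Conclusion.** The concern holds and should be fixed. As written, the only test of the interaction hypothesis either cannot be fitted with the controls included or no longer estimates the randomised interaction. That conclusion follows from the text and the form of the model. The estimate itself need not move: it shifts when app use both differs by subgroup and predicts the outcome.

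Under zero coding, two-fold use and an assumed 10% brochure request rate, a true interaction OR of about 2.0 is reduced to about 1.0, or a false one of about 0.4 to 0.6 appears with 7–18% false rejection. Because power is low anyway, the practical risk is a wrong reading of a subgroup result more than lost power. The primary Z tests in section 9.4.2 carry no covariates, so they and the sample size are untouched.

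**What to change.** Remove app time from the covariate list in section 9.4.7, so that the between-arm and interaction models keep only gender, age, race, smoking status and location. Reconcile section 6.2.1 with sections 2.2 and 6.4 by stating what usage data the developer's server holds, and describe any such data within the app arm only.

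The cost is one deleted phrase and one added statement. No change to conduct, sample size or primary analysis is needed. The only loss is a usage-adjusted between-arm estimate, which would have no randomised interpretation. The change does not rescue the kit-use interaction test, which stays too sparse to be informative at the assumed rates.
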